5.7.1. Overview of Treatment

Summaries for both QWO (CCH-aaes) and mitigation treatments will be provided for the Safety Population.

5.7.1.1. **QWO (CCH-aaes)**

The following information regarding QWO (CCH-aaes) treatment will be summarized for each buttock by cohort:

- Number of QWO (CCH-aaes) treatment sessions per subject
- Number of subjects who received QWO (CCH-aaes) treatment or did not receive QWO (CCH-aaes) treatment each treatment visit
- For subjects who had the QWO (CCH-aaes) treatment done, the number of injections given at each treatment visit
- For subjects who had the QWO (CCH-aaes) treatment done, the subject-level difference in the number of injections given at each treatment visit (left buttock right buttock).

A subject listing containing all QWO (CCH-aaes) treatment administration information will be provided.

5.7.1.2. Mitigation

The following information regarding mitigation treatments will be summarized for the treated buttock(s), by cohort:

• Number of mitigation treatment sessions per subject per QWO treatment cycle

• For subjects who had mitigation treatment done, the type of mitigation treatment received, by treatment visit

Note that for Cohort 2, mitigation treatment was administered to both left and right buttocks. For Cohorts 3-6, mitigation treatment was administered to right buttock only. Cohort 1 did not receive mitigation treatment and therefore will not be included in mitigation treatment summaries.

A subject listing containing mitigation treatment administration information will be provided.

5.7.2. Primary Endpoint and Secondary Endpoints – Bruising Level

For each cohort, results at each level of bruising on the Investigator Assessment of Bruising Severity Scale (see section 2.7.1) will be summarized by visit and by buttock for each subject using counts and percentages. Results and changes from baseline evaluation rating will also be summarized using descriptive statistics (mean and SD).

A listing of Investigator Assessment of Bruising Severity ratings will be provided.

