Disclosure Statement: This is an interventional open-label, post-marketing study to evaluate the effect of mitigation treatments on the bruising induced by QWO (CCH-aaes). The efficacy of the mitigation treatments in reducing bruising and the safety of QWO (CCH-aaes) with mitigation treatments will also be assessed.

Name of Sponsor/Company: Endo Pharmaceuticals Inc.

Name of Marketed Product: QWOTM(CCH-aaes)

Name of Active Ingredient: Collagenase clostridium histolyticum (CCH)

Number of Subjects (planned): A maximum of 75 adult female subjects will be screened in order to enroll 48 adult female subjects into 6 cohorts, such that approximately 45 evaluable subjects complete the study.

Treatment Groups and Duration:

It is intended to enroll 6 treatment cohorts of 8 subjects each. Cohort 1, will receive QWO (CCH-aaes) and no mitigation treatment. Cohorts 2-6 will receive QWO (CCH-aaes) with different mitigation treatments.

Subjects will complete the study on Day 71. The expected duration of subject participation is up to 92 days.

Data Monitoring Committee: No data monitoring committee will be used for this study.

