3. OBJECTIVES AND ENDPOINTS

3.1. Objectives and Endpo	ints
Primary Objective	Primary Endpoint
To assess the effect of mitigation treatments on bruising in the buttocks of subjects with cellulite after the first treatment of QWO (CCH- aaes).	• The proportion of subjects by buttock at each level of bruising on the Investigator Assessment of Bruising Severity Scale, at Day 4, 3 days after QWO (CCH-aaes) injection. This 5-level scale ranges from 0 to 4, with 0 indicating no bruising or almost none, and 4 indicating very severe bruising.
Secondary Objectives	Secondary Endpoints
To assess investigator assessment of bruising with mitigation treatments in subjects with cellulite after the first treatment of QWO (CCH-aaes)	 The proportion of subjects for whom the investigator reported an improvement of bruising on the mitigation treated buttock on Days 4 and 7 as measured on the Investigator-Bruising Improvement Scale (I-BIS), a 3-point Likert scale, with a score on the higher end of the range indicating improvement with treatment. The proportion of subjects by buttock with bruising at each level of the Investigator Assessment of Bruising Severity Scale, by visit. This 5-level scale ranges from 0 to 4, with 0 indicating no bruising or almost none, and 4 indicating very severe bruising.
To assess subject assessment of bruising with mitigation treatments in subjects with cellulite after the first treatment of QWO (CCH-aaes).	 The proportion of subjects treated with QWO (CCH-aaes) reporting an improvement of bruising on the mitigation treated buttock on Days 4 and 7 as measured on the Subject-Bruising Improvement Scale (S-BIS), a 3-point Likert scale, with a score on the higher end of the range indicating improvement of bruising with treatment. The proportion of subjects by buttock bothered by the appearance of bruising on each of their buttocks on the Patient Bother by Bruising Scale, a 4-point scale, with a score of 1 indicating not bothered.
To assess the effect of mitigation treatments on bruising in the buttocks of subjects with cellulite after the first treatment of QWO (CCH- aaes).	• The proportion of subjects by buttock with bruising at each level of the Investigator Assessment of Bruising Severity Scale, by visit. This 5-level scale ranges from 0 to 4, with 0 indicating no bruising or almost none, and 4 indicating very severe bruising.

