Eligible subjects will receive up to 0.84 mg of QWO (CCH-aaes) per buttock in both buttocks for a total dose of 1.68 mg per treatment session for 3 treatment sessions (Day 1, Day 21 \pm 3 days, and Day 43 \pm 3 days). To reduce variance in the bruising observed on the left and right buttock of a subject after the first treatment session of QWO (CCH-aaes), each buttock should be treated with the same number of QWO (CCH-aaes) injections on Day 1, of up to 12 injections per buttock. The number of injections may differ between treatment sessions; 12 injections per buttock during the second and third treatment sessions. The number of injections per buttock per subject may differ among subjects.

Subjects will return to the site on Days 2, 4, 7, and 14 (ie, 1, 3, 6, and 13 days after injection on Day 1) for additional evaluations and digital photography obtained with standardized parameters. After the first mitigation treatment session, on Days 4 and 7, the effect of mitigation treatments on the severity of bruising will be assessed using the Investigator Bruising Improvement Scale (I-BIS) and the Investigator Assessment of Bruising Severity Scale. The effect of mitigation treatments on the severity of bruising will be assessed by subjects on the Subject Bruising Improvement Scale (S-BIS) and the Patient Bother by Bruising Scale. Safety will be assessed by collecting adverse events (AEs) and treatment-emergent adverse events (TEAEs) and assessing injection site reactions in the buttocks throughout the study.

At the investigator's discretion, for the second and third QWO (CCH-aaes) treatment sessions on Days 22 and 43, subjects will be permitted to receive the same mitigation treatment to the right buttock as received during the first QWO (CCH-aaes) treatment session. The severity of bruising will be assessed at each visit. Subject and investigator assessments of satisfaction, aesthetic improvement, and digital photography will also be conducted on Days 22 (\pm 3 days) and 43 (\pm 3 days). Subjects will return to the site for last study visit on Day 71 for additional investigator assessments of bruising and digital photography.

Subjects will participate in the study for approximately 92 days.

Table 2 contains the schedule of assessments.

	Screening Period			Tre	atment Pe	eriod			Follow-Up Period
Procedures	Day -14	Day 1 (Baseline)	Day 2	Day 4	Day 7	Day 14	Day 22 (± 3d)	Day 43 (± 3d)	Day 71/ET (+7d)
Informed consent	Х								

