2.7.3. Investigator Assessment of Bruising Severity Scale

Severity of bruising for each buttock will be documented on the Investigator Assessment of Bruising Severity Scale on Days 1, 2, 4, 7, 14, and 22 (before injection). Investigators will be asked to rate the level of subject bruising using a 5-point photonumeric scale (Table 5):

Rating	Response Option
0	None or almost no bruising
1	Mild Bruising
2	Moderate Bruising
3	Severe Bruising
4	Very Severe Bruising

Table 5:Investigator Bruising Severity Scale

Investigators will document their responses on the corresponding page of the eCRF.

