5. STATISTICAL METHODS

5.1. Overview

The primary efficacy endpoint will be summarized as frequency counts and percentages based on the Evaluable Population by cohort. Mean and standard deviation (SD) will also be provided.

The secondary and supportive efficacy endpoints except for change from baseline measures will be summarized as frequency counts and percentages based on the Evaluable Population by cohort and by buttock, where appropriate. The change from baseline measures will be summarized using descriptive statistics (n, mean, SD, median, minimum and maximum).

TEAEs will be summarized as frequency counts and percentages by preferred term and by cohort. The results and change from baseline for vital signs will be summarized using descriptive statistics.

Subject listings of all data from the eCRFs as well as any derived variables will be presented.

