5.7. Efficacy Evaluation

Efficacy parameters will be summarized for each mitigation group based on the Evaluable Population, unless otherwise stated. Missing values will not be imputed, and only observed data will be summarized.

For mitigation treatments that are bilaterally administered (e.g. compression garments in cohort 2), efficacy parameters will be compared to the control arm (cohort 1). For mitigation treatments that are unilaterally applied (e.g. instant cold packs, arnica patches, INhance, and PDL treatment in cohorts 3-6, which are applied to the right buttock only), subjects will serve as their own control. In these cases, efficacy parameters from mitigation treatment (right buttock) will be compared to contralateral buttock with no mitigation treatment (left buttock). There will be no formal comparison of efficacy parameters between mitigation treatments.

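### The plan fixes which sides and cohorts are compared for bruising severity but not by what measure, and the SAP does not carry the protocol's Day 4 forward as the primary time point

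*SAP*

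**What the plan says.** Protocol 3.1 defines the primary endpoint as "The proportion of subjects by buttock at each level of bruising on the Investigator Assessment of Bruising Severity Scale, at Day 4". The scale runs from 0 (none or almost none) to 4 (very severe). The Disclosure Statement in the synopsis adds that "The efficacy of the mitigation treatments in reducing bruising" will be assessed.

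SAP 2.7.3 has severity rated "on Days 1, 2, 4, 7, 14, and 22 (before injection"). SAP 5.1 states: "The primary efficacy endpoint will be summarized as frequency counts and percentages based on the Evaluable Population by cohort". It then adds: "Mean and standard deviation (SD) will also be provided". SAP 5.7.2 covers the primary and secondary bruising endpoints together: results "will be summarized by visit and by buttock for each subject using counts and percentages", with mean and SD of ratings and of changes from baseline. The shell for Table 14.2.3.1 has separate left and right columns for each cohort and repeats one layout for Days 2, 4, 7, 14 and 22.

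SAP 5.7 fixes the comparators. In Cohorts 3-6 the treated right buttock is compared with the untreated left, and Cohort 2 is compared with Cohort 1. It also says: "There will be no formal comparison of efficacy parameters between mitigation treatments". SAP 8 gives about 48 subjects, six cohorts of about 8, with no power or precision target.

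**The concern.** The objective is to assess the effect of each mitigation, but five proportions on each side do not say what counts as less bruising. A reader can look at any level, any cumulative cut (at least 1, at least 2, at least 3, or 4), the mean, or the change from baseline. These need not agree.

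The comparison in Cohorts 3-6 relies on subjects acting as their own control, yet the severity table gives only left and right margins. By contrast, SAP 3.3.1 and 5.7.1.1 do define and tabulate a left-minus-right difference within subject for injection counts. For the primary outcome, the paired information appears only in the listing.

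The rater is the investigator, who knows which side was treated. Cohorts are small, and there are five mitigation-versus-control readings with no order and no exploratory label. Ruling out formal comparison between mitigations does not touch those five. What is at stake is interpretation: a mitigation could be described as reducing bruising because one row of a large table happened to favour it.

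**Working it through.** **The plan's own figure.** 6 cohorts × 8 = 48, as stated. There are no power inputs to check.

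**Same margins, different readings.** Take one unilateral cohort of 8 with right = 0,0,2,2,2,2,4,4 and left = 1,1,1,1,3,3,3,3. Both means are 16/8 = 2.0.

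| Cut | Right | Left | Favours |
|---|---|---|---|
| ≥1 | 6 | 8 | mitigation |
| ≥2 | 6 | 4 | control |
| ≥3 | 2 | 4 | mitigation |
| 4 | 2 | 0 | control |

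**Margins do not give the paired result.** Paired in the order listed, the differences (right minus left) are −1,−1,+1,+1,−1,−1,+1,+1: 4 subjects lower on the right, 4 higher, SD √(8/7) = 1.07. If the two right-side 4s belong to subjects with left = 1, the two 0s to the other subjects with left = 1, and the four 2s to those with left = 3, the differences are +3,+3 and six of −1: 6 lower, 2 higher, SD √(24/7) = 1.85. The planned severity table is identical in both cases. A t-based 95% half-width is 2.365 × SD/√8 = 0.84 × SD, so 0.89 in the first case and 1.55 in the second.

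**Chance findings with no effect.** The documents give no Day 4 rating distribution, so everything here beyond n = 8 and the 84% is assumed:
- Level 0 = 16%, borrowed from the 84% bruising AE rate in Protocol 2.1 (100 − 84).
- Three splits over levels 0-4: (.16,.21,.21,.21,.21), (.16,.24,.30,.20,.10) and (.16,.34,.30,.15,.05).
- Latent normal ratings with left-right correlation 0.5, 0.7 or 0.9.
- Four unilateral cohorts plus Cohort 2 versus Cohort 1, 40,000 null trials per setting.
- A mitigation looks better if at least 2 of 8 fewer subjects (25 points) reach a cut.

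| At least one of five mitigations looks better at Day 4 | Null trials |
|---|---|
| Any of four cuts, Cohort 2 counted on either buttock | 74-94% |
| Any of four cuts, Cohort 2 on left buttock only | 68-92% |
| One fixed cut (≥2), Cohort 2 on left buttock only | 41-64% |
| Mean rating at least 0.5 lower, Cohort 2 on subject average | 25-67% |

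The second and third rows are the like-for-like comparison.

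**How often cuts conflict.** In one unilateral cohort, some Day 4 cut favours mitigation and another favours control in 35-48% of runs, counting differences of one subject. At 2 of 8 in both directions this falls to 1-6%.

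**Different assumptions.** The second set used moderate-centred, flat and severe-leaning distributions and correlations 0.5-0.85. It allowed three readings: 25 points on rated ≤1, 25 points on rated ≥3, or 0.5 on the mean. Any of the three at Day 4 gives 62-82%. Any of the three at any of Days 2, 4, 7 and 14 gives 91-98%. One fixed Day 4 reading gives 30-59% (rated ≤1) or 31-68% (mean).

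**The case against.** The strongest reply is that the plan is descriptive. It has no test, alpha or success rule, it dichotomises this scale nowhere, and its shell shows every level, cohort and buttock together. That stands, and it makes the problem one of interpretation. A reader might quote a family-wise error of 1 − 0.95⁵ = 0.23, but that refers to five tests nobody plans and counts both directions (favourable only: 1 − 0.975⁵ = 0.12).

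A reader might also infer that the SAP has dropped Day 4. It has not. The protocol still defines Day 4, the SAP tabulates it, and the SAP's table of changes from protocol is empty. One section serves both endpoints because the secondary is the same scale by visit. Nor do other passages set up rival time points. SAP 2 says that "on Days 4 and 7, the effect of mitigation treatments on the severity of bruising will be assessed using" two scales, one of which (I-BIS) has Days 4 and 7 as its own endpoint. Protocol 4.3, on rating during the first treatment session, explains why the investigator rates, and is compatible with Day 4.

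It would also be too strong to say that no contrast exists: the comparators are fixed. Cohorts 3-6 have a direct side-to-side judgement in I-BIS and S-BIS, but these are secondary and do not summarise the severity scale.

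Finally, fixing one statistic does not cure chance findings. A fixed mean contrast of at least 0.5 still appears in 25-67% of null trials. The main cause is n = 8, which is why an interval and an exploratory label are needed as well.

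**Conclusion.** The point holds as a gap in specification that should be closed. The documents say who is compared with whom and, through the protocol, when. They do not say by what measure, and the planned severity table cannot show the within-subject comparison on which four of the five cohorts rely.

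Leaving the Day 4 cut open raises the null chance that some mitigation looks 25 points better from about 41-64% to about 68-94%, or 68-92% like for like. These rates are illustrative. They depend on the assumed distributions, correlations and 25-point threshold, and an AE incidence is only a rough stand-in for a Day 4 rating of 0. The increase appears under both sets of assumptions. The documents do not support a claim that a false finding is close to certain at Day 4, that cuts often conflict by a material amount, or that an error rate is breached.

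**What to change.** In SAP 5.7.2, state:

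- The primary time point is Day 4.
- For Cohorts 3-6 the primary summary is the within-subject difference (right minus left) in Investigator Bruising Severity rating: mean, SD of the difference and 95% confidence interval, with counts of subjects lower, equal and higher on the right.
- For Cohort 2 it is the difference from Cohort 1 in the subject-level average of both buttocks, with 95% confidence interval.
- The Day 4 distribution by level is presented alongside, as the protocol defines it.
- Dichotomised cuts, change from baseline and other visits are supportive.
- The five contrasts are exploratory and reported together. No mitigation is declared effective from a single level, cut or visit.

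SAP 2 and Protocol 4.3 need no change. Because this adds a summary the protocol does not name, enter it in the SAP's table of changes from protocol.

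The cost is a few sentences and one small table shell, from ratings already collected. There are three downsides. A favourable result at another level or visit can only be called supportive. The mean treats the 0-4 scale as equally spaced, as the SAP's mean and SD already do. At n = 8 the intervals will be wide.

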5.7.3. Secondary Endpoints – Improvement of Bruising

For each cohort, results at each rating level of the I-GAIS (see section 2.7.5) will be summarized by visit and by buttock for each subject using counts and percentages, along with mean and SD. Additionally, the 1-level I-GAIS responders (as defined in section 3.4.2.2) will be summarized by cohort and by buttock for each subject using counts and percentages of subjects. A listing of I-GAIS ratings will be provided.

For subjects that receive unilateral mitigation treatments (cohorts 3-6), results at each rating level of the I-BIS (see section 2.7.4) will also be summarized by visit using counts and percentages. A listing of I-BIS ratings will be provided.

For subjects that receive unilateral mitigation treatments (cohorts 3-6), results at each rating level of the S-BIS (see section 2.8.2), as determined by the subject's self-assessment, will be summarized by visit using counts and percentages. A listing of S-BIS ratings will be provided.

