1. STUDY OBJECTIVE

The primary objective of this study is to assess the effect of mitigation treatments on bruising in the buttocks of subjects with cellulite after the first treatment of QWO (CCH-aaes).

The secondary objectives of this study are:

- To assess both investigator and subject assessment of bruising with mitigation treatments in subjects with cellulite after the first treatment of QWO (CCH-aaes);
- To assess the level of aesthetic improvement of cellulite after treatment of QWO (CCHaaes) with and/or without bruising mitigation treatment;
- To assess the safety of QWO (CCH-aaes) with mitigation treatment in subjects with cellulite.

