2.5. Measures to Minimize Bias

This is an open label study, however, the mitigation treatment for each subject will be assigned in a 1:1:1:1:1:1 ratio using a Mitigation Treatment Assignment Table. To ensure a balanced approach in the application of mitigation treatments and the assessment of bruising among the sites and investigators, 1-3 subjects per site will be assigned to each mitigation treatment (pending site capabilities, subjects available, and available mitigation equipment).

At Screening, the investigator or designee will refer to the Mitigation Treatment Assignment Table to determine which mitigation treatment should be administered.

The investigator must maintain a subject master log linking the subject identification number to the subject's name. The subject identification number will not be reassigned to another subject in this study in the case of study withdrawal.

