8. SAMPLE SIZE DETERMINATIONS

The proposed sample size is approximately 48 subjects. The sample size is based on evaluation of mitigation treatment in 6 cohorts of approximately 8 subjects each. Five (5) treatment cohorts will receive mitigation treatments and 1 treatment cohort will not receive mitigation treatment.

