[2] Based on results recorded at the Day 22 visit, before injection.

[3] I-GAIS = Investigator-Global Aesthetic Improvement Scale.

[4] A subject is considered a 1-level I-GAIS Responder if they have an improved (+1, +2, +3) rating on the I-GAIS at an evaluation visit.

Note: By design, Cohort 1 did not receive any mitigation treatment. For Cohort 2, mitigation treatment was administered to both left and right buttocks. For Cohorts 3-6, mitigation treatment was administered to right buttock only.

Evaluable Population includes all enrolled subjects who received at least 1 injection of QWO (CCH-aaes) with or without mitigation treatment and have at least one bruising assessment after the first dose of QWO (CCH-aaes).

Datasets (extraction): status(ddmmmyyyy), Source: ...\xxxxxx.sas

Programming note: please include columns for cohorts 1-2 on page 1, columns for cohorts 3-4 on page 2, and columns for cohorts 5-6 on page 3. Cohort column headers should read: "Cohort 1 No Mitigation", "Cohort 2 Compression", "Cohort 3 Cold Packs", "Cohort 4 Arnica Patches", "Cohort 5 INhance Serum", "Cohort 6 PDL Treatment".

/isit I-BIS Rating [1]	Statistic [2]	Cohort 3 Cold Packs (N=xxx)	Cohort 4 Arnica Patches (N=xxx)	Cohort 5 INhance Serum (N=xxx)	Cohort 6 PDL Treatment (N=xxx)
Day 2					
Number of Subjects Evaluated	n	XX	XX	XX	XX
1 (Worse - more bruising)	n (%)	XX (XX.X)	xx (xx.x)	xx (xx.x)	xx (xx.x)
2 (Similar)	n (%)	XX (XX.X)	xx (xx.x)	xx (xx.x)	xx (xx.x)
3 (Improved - less bruising)	n (%)	xx (xx.x)	xx (xx.x)	xx (xx.x)	xx (xx.x)
Day 4					
Number of Subjects Evaluated	n	XX	XX	XX	XX
1 (Worse - more bruising)	n (%)	xx (xx.x)	xx (xx.x)	xx (xx.x)	xx (xx.x)
2 (Similar)	n (%)	xx (xx.x)	xx (xx.x)	xx (xx.x)	xx (xx.x)
3 (Improved - less bruising)	n (%)	xx (xx.x)	xx (xx.x)	xx (xx.x)	xx (xx.x)
Day 7					
Number of Subjects Evaluated	n	XX	XX	XX	XX
1 (Worse - more bruising)	n (%)	XX (XX.X)	xx (xx.x)	xx (xx.x)	xx (xx.x)
2 (Similar)	n (%)	xx (xx.x)	xx (xx.x)	xx (xx.x)	xx (xx.x)
3 (Improved - less bruising)	n (%)	xx (xx.x)	xx (xx.x)	xx (xx.x)	xx (xx.x)
Day 14					
Number of Subjects Evaluated	n	XX	XX	XX	XX
1 (Worse - more bruising)	n (%)	xx (xx.x)	xx (xx.x)	xx (xx.x)	xx (xx.x)
2 (Similar)	n (%)	xx (xx.x)	xx (xx.x)	xx (xx.x)	xx (xx.x)
3 (Improved - less bruising)	n (%)	xx (xx.x)	xx (xx.x)	xx (xx.x)	xx (xx.x)
Day 22 [3]					
Number of Subjects Evaluated	n	XX	XX	XX	XX
1 (Worse - more bruising)	n (%)	xx (xx.x)	xx (xx.x)	xx (xx.x)	xx (xx.x)

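### The SAP promises a right-versus-left comparison in Cohorts 3-6, but its I-GAIS output gives only separate Left and Right counts in 12 small cells, so the pairing is lost and no with/without or overall summary is formed.

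*SAP*

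**What the plan says.** The secondary objective in SAP Section 1 is "To assess the level of aesthetic improvement of cellulite after treatment of QWO (CCHaaes) with and/or without bruising mitigation treatment". Protocol Section 3.1 attaches to it a subject-level endpoint: the proportion of subjects scoring +1 or better on the I-GAIS on either buttock at Day 71.

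For the cohorts treated on one side only, SAP 5.7 states that "efficacy parameters from mitigation treatment (right buttock) will be compared to contralateral buttock with no mitigation treatment (left buttock"). It names no statistic. The same paragraph rules out formal comparison between mitigation treatments.

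SAP 5.7.3 then plans that "the 1-level I-GAIS responders (as defined in section 3.4.2.2) will be summarized by cohort and by buttock for each subject using counts and percentages". Table 14.2.3.2 follows this for Days 22, 43 and 71, with a Left and a Right column for each cohort. Its programming note reads "please include columns for cohorts 1-2 on page 1, columns for cohorts 3-4 on page 2, and columns for cohorts 5-6 on page 3", which leaves no pooled or Overall column. A footnote states which side was mitigated in each cohort. SAP 3.4.2.2 defines a responder by the rating at a visit and does not say how two buttocks combine into one subject-level result.

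**The concern.** A comparison in which subjects are their own control needs the joint outcome in each subject: both sides improved, right only, left only, or neither. Table 14.2.3.2 prints only the two margins. A reader can see two percentages side by side for each product, but cannot see how many subjects differed between sides or how precisely the difference is known without rebuilding the pairs from Listing 16.2.6.2. In cells of 8, one subject moves the percentage by 12.5 points, so a chance difference in one cohort could be read as a mitigation product helping or impairing the cellulite result.

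The either-buttock endpoint has the same problem, because it too depends on the joint outcome and cannot be recovered from separate Left and Right counts.

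**Working it through.** **Inputs**
- SAP Section 8: a total of about 48, for which the basis given is "The sample size is based on evaluation of mitigation treatment in 6 cohorts of approximately 8 subjects each". No alpha, power, effect size or response rate is given.
- SAP 2.5: equal allocation to the six cohorts.
- Protocol Section 1.1: "such that approximately 45 evaluable subjects complete the study".
- SAP Table 1: Cohorts 3-6 have mitigation on the right only, Cohort 2 on both sides, Cohort 1 on neither.
- Assumption, since the documents give no figure: 20-40% of pairs are discordant on responder status.

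**The plan's own figure.** 6 x 8 = 48, which reproduces the stated size. It is a count of cohorts, with no power calculation behind it.

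**Cells and pairs.** 6 cohorts x 2 sides = 12 cells per visit. One-sided cohorts: 4 x 8 = 32 pairs. With 45 completers spread evenly: 45/6 = 7.5 per cohort and 32 x 45/48 = 30 pairs.

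**What the margins hide.** Suppose a cohort shows 6/8 responders on each side.
- The same 6 subjects may respond on both sides: no discordant pairs, and 6/8 = 75% respond on either buttock.
- Or 4 respond on both, 2 on the right only and 2 on the left only: 4 discordant pairs, and 8/8 = 100% respond on either buttock.

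Table 14.2.3.2 would print the same entries in both cases.

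**Precision of one responder rate (exact Clopper-Pearson 95% CI)**
- 6/8: 34.9% to 96.8%, width 62 points.
- 24/32: 56.6% to 88.5%, width 32 points.

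**Precision of the paired right-minus-left difference.** At a true difference of zero, the approximate 95% half-width is 1.96 x sqrt(discordant fraction / n).

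| Discordance (assumed) | 8 pairs | 32 pairs | 30 pairs |
|---|---|---|---|
| 20% | 31.0 | 15.5 | 16.0 |
| 30% | 38.0 | 19.0 | 19.6 |
| 40% | 43.8 | 21.9 | 22.6 |

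Half-widths are in percentage points. From 8 to 32 pairs the half-width falls by sqrt(32/8) = 2. The formula is a large-sample one and is rough at n = 8, so that column shows scale only.

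**As a test.** With 8 pairs, exact two-sided McNemar needs 6 discordant pairs all in one direction (2 x 0.5^6 = 0.031; five of five gives 0.0625). For an assumed 20-point difference (25% against 5% discordant), power is 0.4% with 8 pairs, 44% with 32 and 40% with 30. For an assumed 30 points (40% against 10%) it is 3.6%, 62% and 59%.

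**The case against.** Several points on the other side are sound.

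- **The objective does not state a contrast.** It asks for the level of improvement, with and/or without mitigation, and gives no hypothesis or margin. A reader might infer that it demands a pooled with-versus-without result and goes unanswered without one. The wording does not support that: it can equally mean describing the response whether or not mitigation was used. A contrast is a reasonable reading, but not a necessary one.
- **Left and Right are already shown side by side.** A reader might infer that the plan has no with/without display at all. That goes too far: each one-sided cohort has both columns and a footnote identifying the mitigated side. What is missing is the pairing, a difference and any summary across cohorts.
- **Reporting by cohort is the protocol's plan.** Protocol 9.3.1 calls for counts and percentages by mitigation group, and the study is descriptive. The cohort columns should therefore stay.
- **The Day 71 pairs are imperfect.** Equal injection counts are specified for Day 1 only (SAP 2.3, 3.3.1), and mitigation at sessions 2 and 3 is at the investigator's discretion (Protocol 4.2). Mitigation is always on the right, and the ratings are open-label. Pooling does not remove these problems. They affect the cohort columns equally, and they are reasons to label the estimate carefully.
- **Pooling averages four different products** and could hide an effect of one. This stands, and is why the pooled figure belongs beside the cohort results.

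The bar on comparing mitigation treatments is no obstacle, since pooled right against left compares no products. None of these points supplies the statistic that SAP 5.7 implies and SAP 5.7.3 and the shell omit.

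**Conclusion.** The point holds as a low-cost improvement. SAP 5.7 commits to a within-subject comparison in Cohorts 3-6 that the I-GAIS text and shell cannot display, because they keep only margins in 12 cells of about 8. Taken at face value, the protocol's either-buttock Day 71 proportion has no row either. No stated number in the plan is wrong.

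Pooling would narrow the approximate 95% half-width of the paired responder difference from 31-44 points to 16-23 points. This rests on the assumed 20-40% discordance, a true difference near zero, and 30 to 32 pairs; the 30 assumes losses are spread evenly over cohorts. A reader might infer that the pooled figure would settle whether mitigation changes the cellulite response. It would not: the interval would still span tens of points, and power for a 20-point difference under the assumptions above is 40-44%. It is a descriptive estimate by session-1 assignment.

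**What to change.** In SAP 5.7.3 and Table 14.2.3.2, keep the cohort columns and add:

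1. For Cohorts 3-6 at Day 71, the right-by-left 2x2 responder counts, by cohort and pooled, with the pooled paired difference and an exact or score 95% CI. Label the block descriptive and by session-1 assignment.
2. An Overall column for all 48 subjects, with the either-buttock Day 71 responder row. State in SAP 3.4.2.2 how two buttocks make one subject-level responder. The Overall column describes the level of response and is not a with/without contrast, since Cohort 2 is mitigated on both sides and Cohort 1 on neither.
3. Cohort 1's right-left difference, as a small check on side.
4. A footnote pointing to the planned summaries of left-right injection differences (SAP 5.7.1.1) and mitigation sessions (SAP 5.7.1.2). It should also state the limits: four products averaged, side confounded with mitigation, open-label ratings, and possible variation in mitigation and injection counts at sessions 2 and 3.

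The cost is a few lines of SAP text and an extra block, column and row in an existing table. No new data are needed. The main risk is over-reading the pooled figure, which the label and the adjacent cohort columns limit.
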